4.4.7 UNSCHEDULED VISITS

Unscheduled visits will be performed if necessary.

4.5 STUDY PROCEDURES

4.5.1 SCREENING AND BASELINE MEASUREMENTS

Screening & Baseline procedures: Participants will present to the screening visit. The cornea sagittal depth/height will be measured with the Visante OCT. OSDI and SPEED will be collected from the participant. Confirmation and change of dry eye status will be assessed based on tear

osmolarity and MMP-9 measurements using the Tearlab Osmolarity System and InflammaDry® test kits respectively. Additionally, their auto-refraction, visual acuity measurements as well as corneal topography with the Pentacam will be carried out. Eligibility will be confirmed, and a baseline biomicroscopy assessment will be performed to assess corneal. (Visit 0-0).

Ocular Surface Imaging: The eyes of the participants will be examined at the slit-lamp biomicroscope and imaged using the Keratograph® 5M. Participants will be seated at the Keratograph® 5M instrument and asked to blink 2-3 times and hold their eyes open for a few seconds until the instrument software takes a picture of the eye. This image acquisition will be repeated twice. This procedure will also be used to assess corneal and conjunctival staining. (Visits 0-0; 1-1; 2-2).

Fitting of the scleral lenses: Participants will be trial fitted with a scleral lens design using the Pentacam software and following the manufacturer's recommendation, but one pair will be ordered non-coated and the other pair will be Hydra-PEG coated (randomly selected). Acceptable fitting will be based on manufacturer's recommended guidelines for fitting these lenses. All scleral lenses used in the study will be made of Boston XO material. Participants will be instructed on insertion, removal, and proper handling of lenses (Visits 0-0, 1-1 2-1).

Imaging procedure With and Without Test Lenses: The anterior segment of the eye and the lens fit will be imaged and assessed using the Visante OCT, Keratograph 5M, Pentacam and Spectralis OCT prior to lens wear and after the lens delivery appointment (Visits 1-1, 2-1), and at the follow up appointment (Visits 1-2, 2-2).

Corneal Thickness Measurements: Corneal thickness will be measured with the Spectralis OCT and Pentacam before and after lens wear (Visits 0-0, 1-2, 2-2). Participants will be seated at the Spectralis OCT and the Pentacam instruments and to blink 2-3 times then hold their eye open for a few seconds until the instrument software takes a measurement of the corneal thickness. This measurement will be repeated twice.

Visual Acuity Assessment: At the screening and follow up appointments (after four weeks of each lens wear), visual acuity will be assessed using the standard LogMAR visual acuity chart. (Visits 1-2 & 2-2).

Contact Lens Dry Eyes, Quality of life assessment and Wearing experience: CLDEQ-8 (biweekly), CLIQ (weekly) and wearing habit/experience along with subjective grading scales (daily) will be used to assess ocular symptoms, quality of life and wearing experience of each of the two pairs of lenses following the four weeks wearing schedule (8-10hrs daily wear). (Visits 1-2, 2-2). These questionnaires will be filled by the participants daily, weekly, and biweekly respectively for each of the pairs of lenses for the four-weeks wearing schedule.

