2 PURPOSE AND HYPOTHESIS

The purpose of this study is to investigate the effects of scleral contact lens wear on a DE population using coated (Hydra-PEG) and uncoated (control) lenses. Symptoms of DE, quality of the tear film, quality of life, epithelial and overall corneal thickness, vision and comfort will be assessed before and after dispensing and wearing the lenses for four weeks.

The hypothesis is that **coated scleral contact lens wear is associated with improved ocular surface health in patients with dry eye disease (DED)**.

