3 OBJECTIVES

The specific objectives are:

1. To evaluate the impact of coated and non-coated scleral contact lenses on DE symptoms.
2. To assess the impact of the lenses on ocular surface health.
3. To measure the comfort and quality of life ratings of each lens type.
4. To determine the subjective ratings of each pair of lenses.

The primary outcome variables are:

1. Epithelial and corneal thickness
2. Quality of the tear film (osmolarity)
3. Levels of protease (inflammatory markers)
4. Contact Lens Impact on Quality of Life (CLIQ) questionnaire score
5. Contact Lens Questionnaire-8 (CLDEQ-8) questionnaire score

Other variables of interest:

- Hours of wear
- Subjective ratings of comfort, dryness, vision and burning.

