4.3.11 STUDY QUESTIONNAIRES-ANALOG RATING SCALES

The following questionnaires will be used in the study.

As part of the recruitment and the baseline measurements (screening visit), Ocular Surface Disease Index (OSDI) and Standardized Patient Evaluation of Eye Dryness (SPEED) questionnaires will be used to determine the severity and frequency of the DE condition. It will also be used to determine eligibility of the participants (Appendix 4 and 5). Contact Lens Dry Eye Questionnaire 8 (CLDEQ-8) will be used to assess ocular symptoms with the scleral contact lenses at the end of each study visit. (Appendix 8) Contact Lens Impact on Quality of Life (CLIQ) will be used to assess the impact of contact lenses on their daily lives during the wearing schedule. The Contact Lens Dry Eye Questionnaire 8 (CLDEQ-8), Contact Lens Impact on Quality of Life (CLIQ) (Appendix 9) and wearing habit/experience log along with the subjective grading scales (Appendix 10) will be given to the participants to fill out for each week wearing the scleral lenses. The questionnaires will be returned to the investigator during the follow up visits. The standard method of recording the CLIQ questionnaire will be used in the study.

Comfort, vision, dryness, burning and overall preference rating scales (0-100) will be used to assess the subjective responses for each of the contact lenses. These subjective ratings will be done on a weekly basis (at home) and at the end of each study visit.

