4.4.2 STUDY VISITS

This study will involve 5 visits over 5 study days in total. The total time commitment for all study visits is approximately 9 hours spread over a 3-month period (See Table 1). The total study visit time commitment may be different for each participant, as the needed visit time will depend on how easily the lenses can be fitted.

The first visit will involve screening and baseline measurements of the participants. The investigator will determine the eligibility of the participant using the inclusion/ exclusion criteria, questionnaires, and tear film analysis (osmolarity and protease levels). Ineligible participants will be discontinued from the study. Eligible participants will be trial fit with the most appropriate scleral lenses (Visit 0-0) as determined by the baseline measurements obtained at the screening visit/appointment. Tear collection from the ocular surface will also be performed as a baseline for comparison with collection from the scleral bowl in the dispensing and follow up visits with the scleral lenses. Participants will be instructed on insertion/application, removal, and proper handling and care of the lenses before dispensing the contact lenses (Visit 1-1, 2-1). Participants will be instructed on insertion, removal, and proper handling and care of the lenses before dispensing the contact lenses (Visit 1-1, 2-1). At each of the lens dispensing/delivery appointments, the researcher will dispense/deliver the study lenses and supplies (contact lens care system). Measurements including visual acuity, topographic corneal clearance, fluorescein assessment will be obtained while the participant is wearing the lenses. The tear collection (from the scleral lens bowl) will be collected immediately the lens is removed from the eye. Study questionnaires (CLDEQ-8, CLIQ and wearing habit/experience log along with the subjective grading scales) will also be handed out to the participants. These questionnaires will be filled each week and biweekly for each of the scleral lens pair for the four weeks wearing schedule.

After the participant has worn the lenses for 8 to10 hours during the day (2 pairs: uncoated scleral contact lens or Hydra-PEG coated scleral contact lens, randomly selected), the participant will return for a follow up visit four weeks later for each pair.

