| Vision assessment | LogMAR chart | Study Visit Form for Scleral Lenses (6) | |
| Lens fit evaluation (Clearance) | Visante and Spectralis | Study Visit Form for Scleral Lenses (6) | |
| Lens Delivery (Visits 1-1, 2-1) | Biomicroscopy/VA | Slit-lamp with camera/LogMAR | Biomicroscopy Form (7) and 6 |
| | LENS INSERTION, ASSESSMENT, DISPENSING AND QUESTIONNAIRE | | |
| | Lens examination | Slit lamp with camera | Study Visit Form for Scleral Lenses (6) |
| | Vision assessment | LogMAR chart | Study Visit Form for Scleral Lenses (6) |
| | Lens fit evaluation (clearance, etc) | Visante, Spectralis | Study Visit Form for Scleral Lenses (6) |
| | Tear Collection | Taken from Bowl of Scleral Lenses | Study Visit Form for Scleral Lenses (6) |

| | | | |
|--|---|-----------------------------------|---|
| | Ocular symptom questionnaire (2x) | Self-Administered Questionnaire | Ocular Symptom Questionnaire (8) |
| | Quality of life questionnaire (4x) | Self-Administered Questionnaire | CLIQ questionnaire (9) |
| | Subjective ratings | Analogue Scales | Wearing Habit Log Form (10) |
| Follow-up visit (Visits 1-2, 2-2) | Vision assessment | LogMAR chart | Study Visit Form for Scleral Lenses (6) |
| | Lens examination | Slit lamp with camera and K5M | Study Visit Form for Scleral Lenses (6) |
| | Lens Fit Evaluation (clearance) | Visante and Spectralis | Study Visit Form for Scleral Lenses (6) |
| | CONTACT LENS REMOVAL, ASSESSMENT, QUESTIONNAIRE REVIEW | | |
| | Tear Collection | Taken from Bowl of Scleral Lenses | Study Visit Form for Scleral Lenses (6) |
| | Biomicroscopy | Slit-lamp with Camera and K5M | Biomicroscopy Form (4) |
| | Sagittal height/topography | Pentacam and Spectralis OCT | Study Visit Form for Scleral Lenses (6) |
| | Osmolarity | Tearlab osmolarity system | Study Visit Form for Scleral Lenses (6) |
| | MMP-9 | InflammaDry | Study Visit Form for Scleral Lenses (6) |
| | Questionnaire Review | CLDEQ-8, CLIQ, Wearing log | Appendices 6,8 and 9 |
| | Participant exists study | - | Remuneration form |

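### The home 0–100 ratings are weekly in 4.3.11 but daily in 4.5.1 (4 or 28 records per lens), and section 9.1 does not name the value that represents each lens

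*Combined protocol and SAP*

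**What the plan says.** - **Section 3 (Objectives).** Objective 4 is "To determine the subjective ratings of each pair of lenses". Objective 3 covers comfort together with quality of life. Hours of wear and the ratings of comfort, dryness, vision and burning are listed as other variables of interest, apart from the five primary outcomes.
- **Section 4.3.11.** The wear log with its grading scales, along with the two questionnaires, "will be given to the participants to fill out for each week wearing the scleral lenses". Of the 0–100 scales (comfort, vision, dryness, burning, overall preference) it adds: "These subjective ratings will be done on a weekly basis (at home) and at the end of each study visit".
- **Section 4.4.2.** The set handed out at delivery includes the log and scales. "These questionnaires will be filled each week and biweekly for each of the scleral lens pair for the four weeks wearing schedule". Daily completion is not mentioned.
- **Section 4.5.1.** The frequency attached to the log and scales is daily: "wearing habit/experience along with subjective grading scales (daily". The paragraph then repeats it: "These questionnaires will be filled by the participants daily, weekly, and biweekly respectively for each of the pairs of lenses". That second sentence gives the frequencies in the reverse order of the forms, but the first leaves no doubt which form is daily.
- **Table 2.** The symptom questionnaire is marked 2x and the quality-of-life questionnaire 4x. The subjective-ratings row has no count.
- **Section 9.1, Table 3.** Comfort ratings are in the parametric row (paired t-test, ANOVA, RM-ANOVA). Dryness and subjective assessment are in the nonparametric row (t-test, Mann-Whitney U). Neither row names a week, a visit, a mean or a time factor for the ratings.

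**The concern.** Site staff cannot follow 4.3.11 and 4.5.1 together, and nothing elsewhere says which prevails. Participants complete the form at home without supervision. If the instruction is unclear, some may rate daily and others weekly, and that cannot be put right afterwards.

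The analysis section leaves a second gap. Even with the frequency settled, each lens would have several ratings per item (home records and visit ratings) and no rule for reducing them to the value that enters the comparison. A paired t-test needs one value per participant per lens. The t-test and Mann-Whitney U test, as listed, take no account of repeated records from one person. The choice of record would therefore be made after the data are seen. At stake is the comparison behind Objective 4 and the comfort part of Objective 3.

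**Working it through.** **Count of records.** Table 2's own counts come first. Over four weeks, a biweekly form gives 4/2 = 2 and a weekly form gives 4 × 1 = 4, which match the 2x and 4x shown. The same arithmetic for the ratings gives:

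- weekly (4.3.11): 4 × 1 = 4 home records per lens per item;
- daily (4.5.1): 4 × 7 = 28 home records per lens per item.

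The four-week period is stated in section 2 ("before and after dispensing and wearing the lenses for four weeks"). Section 4.3.11 also asks for ratings at the end of each visit. With one delivery and one follow-up visit per lens, the totals become about 6 or 30. For the 20 completers in section 4.2.1 and two lenses, the home records per item number 20 × 2 × 4 = 160 or 20 × 2 × 28 = 1,120.

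**Effect on precision when one mean per lens is used.** The documents give no correlation or SD for the ratings, so this part rests on assumptions. Let r be the correlation between one person's lens differences on different occasions, taken as equal for all pairs of occasions, and let every rating be equally precise. Relative to a single rating, the variance of a mean of k differences is (1 + (k − 1)r)/k. The number of participants cancels, so

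SE(4)/SE(28) = √{[(1 + 3r)/4] / [(1 + 27r)/28]}.

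| r | (1 + 3r)/4 | (1 + 27r)/28 | SE ratio |
|---|---|---|---|
| 0.3 | 0.475 | 0.325 | 1.21 |
| 0.5 | 0.625 | 0.518 | 1.10 |
| 0.7 | 0.775 | 0.711 | 1.04 |

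The standard error from weekly collection is thus 4–21% larger than from daily collection.

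**How the choice of summary interacts with the frequency.**

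- The mean of the home ratings in week 4 alone would rest on one rating if weekly and seven if daily. The ratio is √{1/[(1 + 6r)/7]}: √(1/0.400) = 1.58 at r = 0.3 and √(1/0.743) = 1.16 at r = 0.7. That summary depends more on the unresolved frequency (16–58%) than the four-week mean does.
- The four-week visit rating does not depend on the home frequency, but it is a single record. Against a mean of 4, its standard error is larger by √(1/0.475) = 1.45 at r = 0.3 and √(1/0.775) = 1.14 at r = 0.7.

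**The case against.** The strongest case on the other side has four parts.

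1. *The ratings are not primary.* This stands. Section 3 places them under other variables of interest, so neither the five primary outcomes nor the hypothesis on ocular surface health depends on them. Section 9.1 does introduce Table 3 as listing primary outcome variables and includes comfort ratings there, but that does not change their status in section 3.
2. *A time point is already implied.* Section 2 speaks of assessment before and after four weeks of wear, 4.3.11 asks for ratings at each visit, and 4.5.1 ties the assessment to Visits 1-2 and 2-2. The four-week visit rating is a natural candidate, but section 9.1 does not name it.
3. *RM-ANOVA could use every record.* It could, and validly. But Table 3 does not say that it will be applied to the ratings over time, and it lists alternatives that need a single value.
4. *The log may be one sheet per week with daily rows.* The log wording in 4.3.11 permits that reading. The statement that the ratings are done weekly at home does not, so the firm contradiction concerns the ratings.

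A reader might go further and infer that the conflict produces a badly inflated false-positive rate. The documents do not support that. Such inflation would require entering every home record as if independent, which no passage proposes. Inflation from testing each occasion separately would arise equally under a consistent weekly schedule. Nor can it be shown that hours of wear would become a seven-day recall, or that these scales hold the only comfort data: the log and questionnaire forms (Appendices 8 to 10) are not reproduced.

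**Conclusion.** The contradiction is in the current text and nothing else in the documents resolves it: 4 or 28 home records per lens, with visit ratings in addition, and no named value per lens in Table 3. It affects Objective 4 and the comfort part of Objective 3. The quality-of-life part of Objective 3 is outside it, because the CLIQ is weekly in 4.3.11 and 4.5.1 and 4x in Table 2.

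The statistical cost of the frequency itself is modest, a 4–21% difference in standard error for a four-week mean. That figure depends on an assumed exchangeable correlation of 0.7–0.3 and on a weekly rating being as precise as a single daily one. The stronger reasons to act are that the instruction cannot be carried out as written and that the analysed value is left open. The matter should be corrected, but it does not undermine the trial's primary comparisons.

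**What to change.** 1. State one frequency for the 0–100 ratings and one for the wear log, in identical terms in 4.3.11, 4.4.2 and 4.5.1, as a count in Table 2, and on the Appendix 10 form.
2. In section 9.1, name one value per participant per lens for each rating: either the mean of all home ratings over the four-week period or the rating at the four-week visit. The mean is more precise; the visit rating does not depend on the home frequency.
3. Compare the lenses on that value with one paired within-person test, and report the other time points descriptively.
4. Summarise hours of wear in the same way, as one value per participant per lens.

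The cost is small wording changes in four places, a sentence or two in 9.1, and a check that the Appendix 10 form has the fields that the chosen frequency requires. No data beyond those already planned are needed.

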4.5.2 CONTACT LENS DISPENSING/DELIVERY VISIT

Participants will present at the dispensing/delivery visit (visits 1-1, 2-1). The cornea will be assessed with slit lamp biomicroscope. Participant will be asked to insert the contact lenses on the eye. The lens will be examined with the slit lamp biomicroscope with mounted camera. This will be followed by visual acuity and imaging with the Spectralis OCT (to assess corneal clearance and corneal thickness measurements). Before dispensing the contact lens, the investigator will make sure that the participant is confident in inserting/applying, removing and caring for the contact lenses. The appropriate contact lens care system will also be dispensed with the lenses.

The (CLDEQ-8), CLIQ and wearing habit/experience along with subjective grading questionnaires will be administered to the participant to fill out for the four week's wearing period. These questionnaires will be submitted on the next appointment and reviewed for completeness (follow up visit).

4.5.3 FOLLOW-UP VISIT

Following the four weeks of the contact lens wear, the participant will present at the follow-up visit (visits 1-2, 2-2). The lens will be examined with the slit lamp biomicroscope. This will be

followed by visual acuity and imaging with Spectralis OCT (to assess corneal clearance and cornea thickness).

The investigator will carefully remove the contact lens from the eye and immediately collect the tears from the lens bowl for tear analysis. Levels of protease and cytokines in the tears will be assessed.

Slit lamp biomicroscopy mounted camera will be used to assess the corneal integrity and staining. This will be followed by imaging with the Keratograph 5M (for staining) and Spectralis OCT for corneal thickness measurements.

The questionnaire administered (CLDEQ-8, CLIQ and wearing habit/experience along with subjective grading scales) will be collected and reviewed for completeness.

The above-described procedures will be followed for all the lenses to be used in the study.

Table 2 lists a summary of procedures to be conducted at scheduled visits.

Table 2: Summary of procedures at scheduled visits

| Visit | Procedure | Instrument/ application | Form (Appendix #) |
|---|---|---|---|
| Screening, Baseline visit and Trial Lens Fitting (Visit 0-0) | Informed Consent | - | ICL (2) |
| | Demographics & Med. History | - | Screening Form (3) |
| | Ocular surface disease | Self-Administered Questionnaire | OSDI questionnaire (4) |
| | Evaluation of Eye Dryness | Self-Administered Questionnaire | SPEED questionnaire (5) |
| | Vision assessment | LogMAR chart | Study Visit Form for Scleral Lenses (6) |
| | Osmolarity | Tearlab osmolarity system | Study Visit Form for Scleral Lenses (6) |
| | Level of protease (MMP-9) | InflammaDry | Study Visit Form for Scleral Lenses (6) |
| | Tears from ocular surface | Micropipette tear collection kit | Study Visit Form for Scleral Lenses (6) |
| | Ocular surface imaging | Keratograph 5M (K5M) | Study Visit Form for Scleral Lenses (6) |
| | Sagittal height/corneal topography | Visante, Spectralis and Pentacam | Study Visit Form for Scleral Lenses (6) |
| | Biomicroscopy | Slit-lamp with camera | Biomicroscopy Form (7) |
| | Auto-refraction | Auto-refractor | Study Visit Form for Scleral Lenses (6) |
| TRIAL LENS FITTING | | | |
| Lens fitting and examination | Slit lamp with camera | Study Visit Form for Scleral Lenses (6) | |
| Vision assessment | LogMAR chart | Study Visit Form for Scleral Lenses (6) | |
| Lens fit evaluation (Clearance) | Visante and Spectralis | Study Visit Form for Scleral Lenses (6) | |
| Lens Delivery (Visits 1-1, 2-1) | Biomicroscopy/VA | Slit-lamp with camera/LogMAR | Biomicroscopy Form (7) and 6 |
| | LENS INSERTION, ASSESSMENT, DISPENSING AND QUESTIONNAIRE | | |
| | Lens examination | Slit lamp with camera | Study Visit Form for Scleral Lenses (6) |
| | Vision assessment | LogMAR chart | Study Visit Form for Scleral Lenses (6) |
| | Lens fit evaluation (clearance, etc) | Visante, Spectralis | Study Visit Form for Scleral Lenses (6) |
| | Tear Collection | Taken from Bowl of Scleral Lenses | Study Visit Form for Scleral Lenses (6) |

| | | | |
|--|---|-----------------------------------|---|
| | Ocular symptom questionnaire (2x) | Self-Administered Questionnaire | Ocular Symptom Questionnaire (8) |
| | Quality of life questionnaire (4x) | Self-Administered Questionnaire | CLIQ questionnaire (9) |
| | Subjective ratings | Analogue Scales | Wearing Habit Log Form (10) |
| Follow-up visit (Visits 1-2, 2-2) | Vision assessment | LogMAR chart | Study Visit Form for Scleral Lenses (6) |
| | Lens examination | Slit lamp with camera and K5M | Study Visit Form for Scleral Lenses (6) |
| | Lens Fit Evaluation (clearance) | Visante and Spectralis | Study Visit Form for Scleral Lenses (6) |
| | CONTACT LENS REMOVAL, ASSESSMENT, QUESTIONNAIRE REVIEW | | |
| | Tear Collection | Taken from Bowl of Scleral Lenses | Study Visit Form for Scleral Lenses (6) |
| | Biomicroscopy | Slit-lamp with Camera and K5M | Biomicroscopy Form (4) |
| | Sagittal height/topography | Pentacam and Spectralis OCT | Study Visit Form for Scleral Lenses (6) |
| | Osmolarity | Tearlab osmolarity system | Study Visit Form for Scleral Lenses (6) |
| | MMP-9 | InflammaDry | Study Visit Form for Scleral Lenses (6) |
| | Questionnaire Review | CLDEQ-8, CLIQ, Wearing log | Appendices 6,8 and 9 |
| | Participant exists study | - | Remuneration form |

